Document Type	Study Protocol
Document Date	December 12, 2017
Official Title	Proof of Concept study concerning efficacy of P03277 MR Imaging in HCC diagnosis
NCT Number	NCT02973516

Protocol No. GDX-44-008

Proof of Concept study concerning efficacy of P03277 MR Imaging in HCC diagnosis

Phase IIa Clinical Study

Design

Multicenter, exploratory, non randomized, open label, two cohorts, two doses, phase IIa study

EudraCT No.: 2016-002930-62

IND No.: 123673

COORDINATING INVESTIGATORS

1. **What is the primary purpose of the study?** (Please check one box)

For more information, contact the Office of the Vice President for Research and Economic Development at [contact] or [contact].

For more information, contact the Office of the Vice President for Research and the Office of the Vice President for Student Affairs.

11. *What is the primary purpose of the following statement?*

© 2013 Pearson Education, Inc.

SPONSOR

GUERBET, [name]

GUERBET MEDICAL EXPERT

© 2009 by the author

© 2019 Pearson Education, Inc.

PHARMACOVIGILANCE

For more information, contact the Office of the Vice President for Research and the Office of the Vice President for Student Affairs.

Fax: [name]

E-mail: pharmacovig

Confidentiality clause

This document and the information therein are GUERBET's proprietary and confidential information. They shall not be disclosed, disseminated or reproduced, in whole or in part, to any third party, without the prior written consent of GUERBET.

 CONFIDENTIAL	Protocol No. GDX-44-008 Version No.4.0 including amendments 1 and 2 12 December 2017	Page 2 / 64
--	--	-------------

STUDY SYNOPSIS

Study Title: Proof of Concept study concerning efficacy of P03277 MR Imaging in HCC diagnosis	
Protocol No: GDX-44-008	
Study product: P03277 [REDACTED]	Active ingredient: P03277
EudraCT number: 2016-002930-62	IND Number: 123673
Participating countries (Number of sites): Minimum 2 sites in France	
Study objectives Primary objective: To evaluate the diagnostic value for hepatocellular carcinoma (HCC) of P03277 in patients with suspected small nodules and chronic liver disease.	
Secondary objectives: To evaluate multiple quantitative and qualitative efficacy parameters and the safety (clinical and biological) profile of P03277 following single administration in suspected HCC patients	
Study Design and methodology Multi center, exploratory, non randomized, open label, two cohorts, two doses, phase IIa study.	
Number of Subjects / Sample size In total 40 subjects will be included in this exploratory study: 
 - Firstly, 30 subjects in a first cohort with a P03277 dose of 0.1 mmol/kg - Then 10 subjects in a second cohort with a P03277 dose of 0.05 mmol/kg 	
Site selection: The site should have appropriate expertise in liver MR imaging as well as clinical facilities. Investigators should have experience in conducting clinical studies and medical staff should have appropriate level of training.	
Eligibility criteria Selection/inclusion criteria : 
 1. Female or male adult subject aged at least 18 years old or older (subject having reached legal majority age). 2. Subject able and willing to participate to the study. 3. Subject having read the information and having provided his/her consent to participate in writing by dating and signing the informed consent prior to any study related procedure being conducted. 4. Subject presenting with liver cirrhosis or chronic liver diseases as shown by previous liver biopsy or by combination of clinical, endoscopic, biological, ultrasound parameters, and elastography 5. Subject presenting with one to a maximum of 3 untreated hepatic nodule(s) of less than or equal 	

to 3 cm (long axis) previously identified and/or characterized through enhanced CT and/or MRI within a maximum of 21 days before P03277 imaging, confirmed for HCC or not

6. Female subject must be using a medically approved contraception method* detailed below or be surgically sterilized or post-menopausal (>12 months amenorrhea)

** medically approved contraception methods include: female sterilization, barrier methods of contraception (condom or occlusive cap (diaphragm or cervical/vault caps) with spermicidal foam/gel/film/cream/ vaginal suppository), use of oral, injected or implanted hormonal methods of contraception or other forms of hormonal contraception that have comparable efficacy (failure rate <1%), for example hormone vaginal ring or transdermal hormone contraception, placement of an Intrauterine Device (IUD) or Intrauterine System (IUS).*

7. Subject affiliated to national health insurance according to local regulatory requirement

To be selected and included in the study, the subject must meet all these inclusion criteria.

Non-selection/non-inclusion criteria

1. Pregnant or breast-feeding female subject (a female subject of childbearing potential or with amenorrhea for less than 12 months must have a negative urine or serum pregnancy test within 24 hours prior to study MRI)
2. Subject presenting with hepatic nodule more than 3 cm in addition to nodule(s) less than or equal to 3 cm
3. Subject already treated for HCC by surgery or thermal ablation for which the resection or coagulation area is less than 2cm from the new nodule(s)
4. Subject previously treated by transarterial chemoembolization
5. Subject with moderate or severe renal impairment (eGFR < 60 mL/min/1.73m²) based on measurement done or available within the 7 days before P03277 administration and assessed after any iodinated contrast agent administration, or with dialysis end stage renal disease (ESRD)
6. Subject with known class III/IV congestive heart failure according to the New York Heart Association classification
7. Subject having received or is scheduled to receive any contrast agent within 7 days before P03277 planned administration date and within 3 days after P03277 planned administration date.
8. Subject with known contra-indication(s) to the use or with known sensitivity to drugs from a similar pharmaceutical class as P03277
9. Subject having received any investigational medicinal product within 7 days prior to P03277 planned administration date
10. Subject presenting with any contraindication to MRI examination (see recommendations of the French Society of Radiology)
11. Subject having planned palliative/treatment interventions for the suspected nodules (radiotherapy, chemotherapy or others) during the study period except for biopsy/surgery
12. Subject related to the investigator or any other study staff or relative directly involved in the study conduct

 CONFIDENTIAL	Protocol No. GDX-44-008 Version No.4.0 including amendments 1 and 2 12 December 2017	Page 4 / 64
--	--	-------------

13. Subject previously enrolled in this study
14. Subject with anticipated, current or past condition (medical, psychological, social or geographical) that would compromise the subject's safety or her/his ability to participate in the study.
15. Subject unlikely to comply with the protocol (e.g., uncooperative attitude, inability to return for follow-up visits and/or unlikelihood of completing the study).
16. Vulnerable subject according to article L1121-6 of the French Public Health Code,
17. Subject under guardianship or unable to give his/her consent according to the article L1121-8 of the French Public Health Code

Subjects presenting with one or more of these non-inclusion criteria must not be selected and included in the study.

Investigational Medicinal Product administration:

One single injection of P03277 to be administered with a power injector as an IV bolus at 2 mL/sec followed by a 0.9% saline flush at the same injection rate:

- at a dose of 0.1 mmol/kg for the first cohort (30 subjects),
- at a dose of 0.05 mmol/kg for the second cohort (10 subjects).

Study duration

Subject participation duration could be from 2 days up to 3 months approximately

- The maximal period between subject screening and P03277 administration in the trial is 7 days but can be the same day if eGFR measurement within the last 7 days is available.
- Subject inclusion will be confirmed the day of administration with P03277 according to the eGFR results and urinary pregnancy test if applicable
- Subject will be followed up at +1 day safety visit
- Optionally and according to standard of care for histology analysis locally, the subject will have a specific biopsy or a surgically resected specimen collected at the time of loco-regional treatment. This procedure, whatever the type (biopsy, surgery), should be done between 3 days after P03277 administration and 13 weeks maximum. Alternatively it is acceptable to record results from histology done within 2 months prior to P03277 administration.

The study will be considered as completed once all the images collected for all the subjects will have been reviewed by expert readers.

Imaging Protocol

1.5 T and 3T MR equipments will be accepted. The same machine for each site should be used all along the study. Automatic real time bolus tracking will be used.

Standard Axial MR sequences will be used for pre-injection and post injection imaging.

- **Unenhanced imaging sequences:**
 - GRE T1 in- and opposed-phase sequence
 - 3D GRE T1 sequence with fat saturation
 - FSE T2 sequence with fat saturation (can be done after injection)
- **Contrast-enhanced imaging sequences - Post P03277 injection**
 - 3D GRE T1 sequences with fat saturation acquired during 3 time-points i.e. during arterial

(bolus track synchronization), portal (approx. 70-80 sec post injection) and delayed (3 minutes post injection) phases

- 3D GRE T1 sequences with fat saturation acquired at 15 ± 5 minutes
- 3D GRE T1 sequences with fat saturation will be performed at 20mn, 1hour and 2 hours post-injection for the first 5 subjects and then possibly extended to next subjects if significant liver parenchyma enhancement is depicted.

Evaluation criteria:

Primary criteria:

- **Nodule diagnosis at P03277 imaging** (HCC, not HCC specify) will be assessed:
 - on a maximum of 3 hepatic nodules per subject
 - based on visual qualitative analysis of P03277 triphasic imaging (arterial, portal and delayed imaging) showing HCC typical hallmarks according to EASL/EORTC criteria (arterial hypervascularization and portal wash-out or delayed wash-out)
 - by two expert readers. In case of discordance, a consensus diagnostic will be obtained
- **The standard of reference** for diagnosing liver nodules (HCC, other malignant, regenerative or dysplastic nodule, benign, uncertain) will be assessed by the site according to their standard of care and according to adapted EASL/EORTC diagnostic criteria, considering previous contrast enhanced imaging (CT and/or MRI) and/or histology analysis and/or the more recent AFP measurement available:

HCC will be considered when:

- Histology is positive for HCC
- Or nodule identified and characterized by typical features using two different triphasic contrast enhanced modalities. Typical features are arterial hypervascularization and portal wash-out or delayed wash-out
- Or $AFP > 200\text{ng/mL}$ in a presence of a single nodule

Other diagnosis than HCC could be based on imaging only and/or histology.

Secondary criteria:

Secondary criteria will consist of both efficacy and safety evaluations in participating subjects:

Secondary efficacy criteria (by on-going on-site and/or expert reading):

- **Technical adequacy of images (on going on-site and expert reading):** adequate, yes/no and reason for inadequate recorded (artifact due to subject, artifacts due to the machine, artifacts due to contrast agent, injection technical failure, other specify)
- **Visualization of biliary and liver vascular abnormalities (expert reading):** presence of portal thrombosis, hepatic venous thrombosis, biliary tract invasion, and visualization of arterio-portal fistula.
- **Number of liver nodules detected (on going on-site and expert reading)**
- **Qualitative evaluation (expert reading)**
 - At each phase (unenhanced, arterial, portal, delayed, 15 ± 5 minutes): nodule (maximum of 3) intensity relative to parenchyma according to the scale: hypointense, hyperintense or isointense (and relative to spleen on T2 if hyperintense); In addition nodules will be described as homogeneous or heterogeneous
 - Presence of fat and Iron within liver nodules at unenhanced in and opposed phase GRE sequence
 - Visualization (yes/no) of a perilesional capsule at portal or delayed phase or at 15 ± 5

minutes

- **Quantitative evaluation (on going on-site):**
 - At each phase, (unenhanced, arterial, portal, delayed, 15 ±5 minutes) SI measurement using ROIs placement in nodule (maximum of 3), liver, and background for SNR, CNR, percentage of nodule enhancement (PE)
 - On arterial and on portal phase, SI measurement of the aorta and the portal vein maximum vessel enhancement for SNR calculation purpose
- **Qualitative evaluation (expert reading)** for each available very delayed images (20mn, 1h, 2h) of any liver enhancement (hyperintense, isointense, hypointense) relative to the unenhanced fat-suppressed GRE T1 sequence and of nodule enhancement relative to parenchyma.

Clinical and biological safety criteria:

- **For screening purpose**, the subject will have physical examination (performed by a physician), vital signs (systolic and diastolic blood pressure in supine position, pulse rate), eGFR measurement locally if not available within 7 days before P03277 administration. Urine or blood sample for pregnancy test for women with childbearing potential should be done within 24 hours prior to study MRI.

The following evaluation will be done during the subject participation:

- **Vital signs** (blood pressure, pulse rate): Before P03277 administration, 30 +/- 5 min after drug administration, and at Day +1 for all subjects
- **Biochemistry tests** by central lab at screening visit or inclusion visit and after P03277 administration at Day+1 for all subjects: sodium, potassium, chloride, random glucose, Blood Urea Nitrogen (BUN) / urea, creatinine, eGFR, Cystatin C, total protein, calcium, phosphorus, total bilirubin, conjugated bilirubin, unconjugated bilirubin, Aspartate Amino Transferase (AST), Alanine Amino Transferase (ALT), alkaline phosphatase, Lactate DeHydrogenase (LDH), Triglycerides (TG).
- **Hematology tests** by central lab at screening visit or inclusion visit and after administration at Day+1 for all subjects : Red Blood Cells (RBCs), White Blood Cells (WBCs), neutrophils, eosinophils, basophils, lymphocytes and monocytes, platelet count, hemoglobin, hematocrit, Mean red blood Cells Volume (MCV).
- **Tolerance at the injection site** will be recorded from time of administration of P03277 up to 30 minutes post administration and 1 day after injection.
- **Adverse event (AE)** will be recorded throughout the subject participation until the +1day safety FU. Only AE that the investigator considers as related to P03277 and/or the study procedures will be recorded at the optional Visit 4 between 3 days after P03277 administration up to 3 month.

Statistical methods:

For primary endpoint: descriptive analysis of P03277 MRI sensitivity and specificity results using standard of reference will be presented by dose.

Descriptive statistics will be provided for secondary efficacy endpoints will be presented by dose and clinical and biological safety and will presented by dose and overall.

 CONFIDENTIAL	Protocol No. GDX-44-008 Version No.4.0 including amendments 1 and 2 12 December 2017	Page 7 / 64
---	--	-------------

STUDY FLOW CHART

[figure not shown]
Visit	Screening (V1)	Inclusion and P03277 liver imaging visit (V2)					Safety follow-up (V3)	Biopsy /procedure for specimen histology (V4 optional as per standard of care)	
Timing	-7 to -0 days	Inclusion Day 0	Pre-injection	Dosing	Acquisition of triphasic MRI sequences	30mn	Optional very delayed acquisition	Day +1	Between 3 days after V2 and up to 13 weeks
Informed consent signature	x								
Eligibility criteria (1)	x	x							
Physical examination (2)	x								
Demographic data	x								
Medical history	x								
Chronic liver disease status	x								
Previous imaging results and AFP measurement collected for reference diagnosis	x	x							
Proposed diagnosis according to available examinations for standard reference (excluding histology and P03277 images)								x	
Biopsy histologic analysis for reference diagnosis (3)									x
Body weight		x							
Concomitant treatments	↔								
Pregnancy test (4)	x	x							
Vital signs (BP, HR) (5)	x	x				x		x	
Blood samples for laboratory parameters (6)	(x)	x						x	
e-GFR for screening (7)	x								
IP administration			x						
MRI examination (8)			x	x		(x)			
Injection-site tolerance (9)					↔		x		
Adverse events (AEs) (10)	↔								(x)

- (1) Inclusion criteria checked at the screening visit must be confirmed at the inclusion visit.
- (2) Physical examination should be performed by a physician: examination of general appearance, skin, neck (including thyroid), eyes, ears, nose, throat, lungs, heart, abdomen, back, lymph nodes, extremities, vascular and neurological. Information indicating the global assessment (normal or abnormal (specify) of the physical examination should be recorded on source documentation.
- (3) It is acceptable to record results from histology done within 2 months prior to P03277 administration
- (4) Urinary or serum pregnancy test for woman of childbearing potential to be performed at inclusion. Results must be negative to continue in the trial.
- (5) Vital signs (blood pressure, pulse rate).

Guerbet  CONFIDENTIAL	Protocol No. GDX-44-008 Version No.4.0 including amendments 1 and 2 12 December 2017	Page 8 / 64
--	--	-------------

[figure not shown]
- (6) Biochemistry and hematology tests to be done by central lab. Baseline can be done at screening or inclusion visit.
- (7) e-GFR to be done by local Lab, and results must be available prior to administration of P03277
- (8) MRI examination includes unenhanced sequences and triphasic post-injection sequences (arterial, portal, delayed, 15 ±5 minutes). Very delayed sequence will be performed at 20mn, 1hour and 2 hours post-injection for the first 5 subjects and then possibly extended to next subjects if parenchyma enhancement is visualized
- (9) Injection-site tolerance monitoring is to be assessed from injection up to 30 minutes post injection and then at day +1 after administration.
- (10) AEs will be assessed beginning with subject's informed consent signed and will end after the last follow up evaluation at day+1 after injection, and /or over a longer period if the investigator becomes aware of an adverse reaction/serious adverse reaction. At the time of optional visit 4, adverse event considered as related to the product/to the study should be reported in the study database.

STUDY DIAGRAM

The maximum duration of the study for the subject will be 14 weeks.

The study will be considered as completed once all the images collected for all the subjects will have been reviewed by expert readers.

 CONFIDENTIAL	Protocol No. GDX-44-008 Version No.4.0 including amendments 1 and 2 12 December 2017	Page 11 / 64
--	--	--------------

ABBREVIATIONS

AE	Adverse Event
AFP	Alpha fetoprotein
AR	Adverse Reaction

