3.2 Study Duration

Subject participation duration could be from 2 days up to 3 months approximately

- The maximal period between subject screening and P03277 administration in the trial is 7 days but can be the same day if eGFR measurement within the last 7 days is available.
- Subject inclusion will be confirmed the day of administration with P03277 according to the eGFR results and urinary pregnancy test if applicable
- Subject will be followed up at +1 day safety visit
- Optionally and according to standard of care for histology analysis locally, the subject will have a specific biopsy or a surgically resected specimen collected at the time of loco-regional treatment. This procedure, whatever the type (biopsy or surgery), should be done between 3 days after P03277 administration and 13 weeks maximum. Alternatively it is acceptable to record results from histology done within 2 months prior to P03277 administration.

The study will be considered as completed once all the images collected for all the subjects will have been reviewed by expert readers.

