4.2 Non Inclusion Criteria

1. Pregnant or breast-feeding female subject (a female subject of childbearing potential or with amenorrhea for less than 12 months must have a negative urine or serum pregnancy test and within 24 hours prior to study MRI).
2. Subject presenting with hepatic nodule more than 3 cm in addition to nodule(s) less than or equal to 3 cm
3. Subject already treated for HCC by surgery or thermal ablation for which the resection or coagulation area is less than 2cm from the new nodule(s)
4. Subject previously treated by transarterial chemoembolization
5. Subject with moderate or severe renal impairment (eGFR < 60 mL/min/1.73m²) based on measurement done or available within the 7 days before P03277 administration and assessed after any iodinated contrast agent administration, or with dialysis end stage renal disease (ESRD)
6. Subject with known class III/IV congestive heart failure according to the New York Heart Association classification

 CONFIDENTIAL	Protocol No. GDX-44-008 Version No.4.0 including amendments 1 and 2 12 December 2017	Page 27 / 64
---	--	--------------

7. Subject having received or is scheduled to receive any contrast agent within 7 days before P03277 planned administration date and within 3 days after P03277 planned administration date.
8. Subject with known contra-indication(s) to the use or with known sensitivity to drugs from a similar pharmaceutical class as P03277
9. Subject having received any investigational medicinal product within 7 days prior to P03277 planned administration date
10. Subject presenting with any contraindication to MRI examination (see recommendations of the French Society of Radiology)
11. Subject having planned palliative/treatment interventions for the suspected nodules (radiotherapy, chemotherapy or others) during the study period except for biopsy/surgery
12. Subject related to the investigator or any other study staff or relative directly involved in the study conduct
13. Subject previously enrolled in this study
14. Subject with anticipated, current or past condition (medical, psychological, social or geographical) that would compromise the subject's safety or her/his ability to participate in the study.
15. Subject unlikely to comply with the protocol (e.g., uncooperative attitude, inability to return for follow-up visits and/or unlikelihood of completing the study).
16. Vulnerable subject according to article L1121-6 of the French Public Health Code,

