7.2.2 Safety assessment

The safety assessments will be based on the following: Adverse Events (AEs), injection site tolerance, clinical laboratory parameters (blood), vital signs. A central laboratory will be used to analyze and report blood chemistry/hematology. eGFR would also have been evaluated locally only for screening. eGFR evaluated centrally will be used for safety evaluation.

- **Adverse events**

Adverse Event monitoring will be recorded until Day+1. After, AEs that the investigator considers related to P03277 and/or study procedures will be recorded at optional V4.

- **Injection-site tolerance**

For all subjects, injection-site tolerance (burning, pain, eruption, extravasation, inflammation, or other) will be assessed over 1 day following each contrast agent injection (during the injection up to 30 ± 5 mn, and the day after injection) and over a longer period if the investigator becomes aware of any related AE. In case of injection-site pain, the subject will be asked to specify the level of pain using a visual analogic scale (VAS, [REDACTED]) from 0 (no pain) to 10 (maximal pain).

- **Clinical laboratory parameters**

For each subject, blood samples will be performed at baseline and Day+1 for being analyzed by a central laboratory.

The following parameters will be obtained and assessed:

- Hematology: Red Blood Cells (RBCs), White Blood Cells (WBCs), neutrophils, eosinophils, basophils, lymphocytes and monocytes, platelet count, hemoglobin, hematocrit, Mean red blood Cells Volume (MCV).
- Biochemistry: sodium, potassium, chloride, random glucose, Blood Urea Nitrogen (BUN) / urea, creatinine, eGFR, Cystatin C, total protein, calcium, phosphorus, total bilirubin, unconjugated and conjugated bilirubin, Aspartate Amino Transferase (AST), Alanine Amino Transferase (ALT), alkaline phosphatase, Lactate DeHydrogenase (LDH). Triglycerides (TG).

In female subjects of childbearing potential, a urine or serum pregnancy test will be performed on-site prior to the administration of IMP.

For all other laboratory assessments, the central laboratory will flag laboratory values falling outside of the normal ranges on the central laboratory report (which the investigator should review and sign off) and the investigator will report any values considered clinically significant as an AE or alternatively according to investigator's judgement as medical history if measured at baseline and related to an underlying disease.

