Guerbet  CONFIDENTIAL	Protocol No. GDX-44-008 Version No.4.0 including amendments 1 and 2 12 December 2017	Page 35 / 64
--	--	--------------

- **Vital signs**

Vital signs (systolic and diastolic blood pressure in supine position, pulse rate) will be measured and recorded according to the following schedules:

- Immediately prior to each contrast agent injection (baseline value)
- At 30+-5 minutes following P03277 injection
- One day after P03277 injection

If significant changes in vital signs occur, vital signs should be recorded more frequently, and for as long as necessary, to ensure that the changes have been resolved and/or that the subject is stable. All clinically significant abnormal value or change value will be recorded as AEs or alternatively according to investigator's judgement as medical history if measured at baseline and related to an underlying disease.

A significant clinically change is defined as follows: Pulse Rate < 40 or >100 bpm; systolic Blood Pressure < 90 or >160 mmHg; diastolic Blood Pressure > 100 mmHg.

Blood pressure and pulse rate will be measured after a rest of 10 minutes in supine position. Blood pressure will not be measured on the arm used for the injection.

 CONFIDENTIAL	Protocol No. GDX-44-008 Version No.4.0 including amendments 1 and 2 12 December 2017	Page 36 / 64
---	--	--------------

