 - Contrast enhanced imaging modalities used for characterization (CT and/or MRI), type of contrast agent used for MRI (extracellular, hepatospecific), date of acquisition and, for each of nodules if HCC typical hallmark is visualized according to EASL/EORTC criteria and in case of MRI using hepatospecific contrast agent, also if hyperintensity of parenchyma relative to the nodule is seen.
 - The more recent AFP measurements available and date
- **Biopsy or intervention for specimen surgery** scheduled for histology analysis. The planned date should be recorded.
- A **urine or serum pregnancy test** for all women of childbearing potential should be done and must be negative;
- **Verification of eligibility criteria**. Criteria relative to eGFR measurement may not be available at screening ;

 CONFIDENTIAL	Protocol No. GDX-44-008 Version No.4.0 including amendments 1 and 2 12 December 2017	Page 38 / 64
---	--	--------------

- Schedule of **blood sample collection for serum creatinine** dosage if applicable, in order to obtain the results and calculate eGFR at the time of inclusion at the latest;
- If done at screening, **blood samples for baseline hematology/biochemistry tests** will be collected according to central laboratory manual. If not done at screening, they have to be scheduled at inclusion visit (V2).
- Recording the subject screening visit in the CRF.

9.1.2 Inclusion Visit – Visit 2 – Day 0

Inclusion visit can be the same day as screening if all eligibility criteria can be verified the same day.

During this visit, the following tasks or assessments will be performed:

- **Verification of inclusion and non-inclusion criteria** by the Investigator; creatinine results for eGFR calculation should be available before P03277 administration.
- **A urine or serum pregnancy test** for female subject of childbearing potential will be performed prior to P03277 administration and must be negative (do not perform the test if a negative pregnancy test result performed within 24 h prior to the MRI is available);
- Any changes in **concomitant treatments** since the last visit will be documented;
- **Any AE** occurred since the last visit will be documented
- If not already done at screening, **blood samples for baseline haematology/biochemistry tests** will be collected according to central laboratory manual;
- Measurement of **body weight**;

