A table will be presented showing the total numbers of AEs and SAEs and the distribution of AEs (number [%] of subjects with 0, 1, 2 etc... AEs) . The table will also show the same information for SAEs defined as TEAEs with serious classified as 'yes' or missing, unless the number of SAEs make this uninformative.

Summaries by System Organ Classes (SOC) and Preferred Term (PT)

The table of summaries of at least one TEAE will be repeated by SOC only (without the breakdown by PT).

Concomitant medication after P03277 administration

Concomitant medications will be coded using the WHO Drug dictionary and be presented displaying number and frequency by ATC System Main Group and Therapeutic Subgroup.

Guerbet  CONFIDENTIAL	Protocol No. GDX-44-008 Version No.4.0 including amendments 1 and 2 12 December 2017	Page 53 / 64
--	--	--------------

Injection site tolerance

Number of subjects experiencing burning, pain, eruption, extravasation and inflammation at site injection will be tabulated. Pain at injection site will be measured using the Visual Assessment Scale (VAS) and VAS measurements for these subjects will be tabulated.

Laboratory data

The statistical analysis will present results in standard international units and United States units. Original units will be only listed. Laboratory data will be analyzed quantitatively and qualitatively. Qualitative analyses will be done via comparison of laboratory data to their reference ranges and according to their clinical significance. Quantitative analyses will be done by tabulating raw data and change from baseline. They will be displayed qualitatively as well as by means of shift tables.

Vital signs

Vital signs will be analyzed quantitatively and qualitatively. Qualitative analyses will be done via comparison of vital signs data to their normal ranges (see section 7.2.2) and according to their clinical significant changes. Quantitative analyses will be done by tabulating raw data and change from baseline.

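### The central-laboratory safety baseline may be drawn up to 7 days before P03277, so change from baseline for subjects sampled early in screening cannot be attributed cleanly to the product

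*Protocol*

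**What the plan says.** Footnote (6) to the protocol's flow chart covers the central biochemistry and haematology samples: "Baseline can be done at screening or inclusion visit". The synopsis gives the same choice. Section 9.1.2 makes the Visit 2 sample conditional: "If not already done at screening, blood samples for baseline haematology/biochemistry tests will be collected according to central laboratory manual". Each subject therefore has one baseline sample.

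Section 3.2 sets the window: "The maximal period between subject screening and P03277 administration in the trial is 7 days but can be the same day". Section 7.2.2 gives the full laboratory schedule: "For each subject, blood samples will be performed at baseline and Day+1 for being analyzed by a central laboratory". The same section uses the central eGFR, not the local screening value, for safety evaluation. For vital signs it places the baseline directly before injection.

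In Section 12.4, under laboratory data: "Quantitative analyses will be done by tabulating raw data and change from baseline". Shift tables, reference-range comparison and clinical significance are also planned, and safety results are shown by dose and overall.

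Two rules govern earlier contrast. Section 4.1, criterion 5, requires nodules seen on enhanced CT and/or MRI no more than 21 days before P03277 imaging. Section 4.2, criterion 7, excludes: "Subject having received or is scheduled to receive any contrast agent within 7 days before P03277 planned administration date". That period is tied to the dosing date.

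**The concern.** The study has no control arm (Section 3.1), so the before-and-after difference within a subject is the only contrast that bears on a laboratory effect of P03277. It can be read that way only if the first sample reflects the subject's state just before injection.

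A baseline drawn early in screening does not ensure this. The difference then also contains whatever happened between that sample and dosing: drift in chronic liver disease, or recovery from or development of an effect of the earlier contrast scan. The protocol itself treats earlier contrast as relevant to renal values, since Section 4.2, criterion 5, requires the eligibility eGFR to be measured after any iodinated contrast. It sets no minimum gap between contrast and the safety baseline.

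The error can go either way. A rise before dosing would look like a product effect. A baseline still disturbed by earlier contrast could recover and hide a real rise. Where the only baseline is from screening, no analysis can recover the missing Day 0 value, so the statistical analysis plan cannot repair this.

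**Working it through.** **Inputs.** Screening Day -7 to Day 0 (flow chart, Section 3.2). Dosing Day 0. Only post-dose draw Day +1 (Sections 7.2.2 and 9.1.3). Earlier enhanced imaging at most 21 days before P03277 imaging (Section 4.1). No contrast within 7 days before dosing (Section 4.2). In total 40 subjects, 30 and 10 (Section 8).

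**Check of the window against a figure in the plan.** The study diagram gives a maximum duration of 14 weeks. Seven days of screening plus 13 weeks to the optional Visit 4 is 7 + 13 × 7 = 98 days, and 98 / 7 = 14.0 weeks. The plan's own total therefore uses the full 7-day screening window.

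**Baseline to Day +1.** With the baseline on day b, the interval is 1 − b.
- b = 0: 1 − 0 = 1 day.
- b = −7: 1 − (−7) = 8 days, of which 7 precede dosing. That is 7/8 = 87.5% of the elapsed days.

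**What the difference contains.** Writing Y(d) for the value on day d:

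Y(+1) − Y(b) = [Y(+1) − Y(0)] + [Y(0) − Y(b)].

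The first bracket is the post-dose change. The second is the pre-dose change. It is zero by construction only when b = 0, and it is not observed when the only baseline comes from Visit 1.

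**Earlier contrast to baseline.** With contrast on day c, the gap is b − c. Whether contrast on Day -7 itself is excluded depends on how the 7-day rule is read, so both readings are shown. Permitted day pairs are 8 baseline days times the number of permitted contrast days.

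| | Last contrast Day -8 | Last contrast Day -7 |
|---|---|---|
| Permitted pairs | 8 × 14 = 112 | 8 × 15 = 120 |
| Gap, baseline at V1 or V2 | 1 to 21 days | 0 to 21 days |
| Pairs with gap of at most 1 day | 1 | 3 |
| Pairs with gap of at most 3 days | 6 | 10 |
| Gap, baseline on Day 0 only | 8 to 21 days | 7 to 21 days |

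These counts describe which schedules are allowed. They are not probabilities.

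**Which outputs depend on b.** Change from baseline and shift tables do. Raw Day +1 values, their comparison with reference ranges and the review for clinical significance do not.

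**The case against.** The strongest reply is that nothing here is contradictory. The choice of visit is stated consistently and is bounded at 7 days. The flow chart marks the sample in brackets at screening and without brackets at inclusion, which reads as inclusion by default. Screening and inclusion may fall on the same day, and the issue then disappears. Nobody may be affected. The analysis is descriptive and no test is planned (Section 8), so no error rate is at risk. A Visit 1 sample also gives the investigator a central result before dosing, and reporting the baseline day and the time since contrast would expose affected subjects without an amendment.

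Most of this stands, and it limits the point to a minor one. It does not remove it: the text permits the early baseline, and reporting the timing identifies affected subjects without supplying the missing value.

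A reader might infer more than the documents support:
- That the whole laboratory evaluation is confounded. Three of the planned presentations do not use the baseline.
- That 88% of a measured change may precede dosing. The 7/8 is a share of days; nothing in the protocol converts days into change.
- That laboratory shifts pass automatically into the treatment-emergent tables. The rule in Section 12.4 that resolves doubt towards treatment emergence concerns adverse events. A laboratory value becomes one only if the investigator judges it clinically significant (Sections 7.2.2 and 9.5.1).
- That the dose cohorts differ in baseline timing. The protocol gives no sign of this.

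**Conclusion.** The point holds in limited form. For subjects whose single central baseline is drawn early in screening, change-from-baseline and shift results cover up to 8 days, only the last of which follows P03277. In the extreme corner of the windows they start about one day after an earlier contrast scan. Those results cannot be attributed cleanly to the product.

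The size of any distortion cannot be calculated, because the protocol gives neither laboratory variability nor the size of an effect of earlier contrast. The number of subjects is unknown, from 0 to 40. That an earlier scan or a week of liver disease moves these values is an assumption, although the timing condition on the eligibility eGFR shows that the plan takes earlier contrast into account. Severity is minor: a cheap improvement to data that cannot be recovered afterwards.

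**What to change.** In the synopsis, flow-chart footnote (6) and Sections 7.2.2, 9.1.1 and 9.1.2, require the central biochemistry and haematology baseline to be drawn at Visit 2 before injection in every subject, and remove the Visit 1 option. Name that sample as the baseline for change and shift tables. Keep the local screening creatinine/eGFR for eligibility only. This makes mandatory the draw that the flow chart already marks at inclusion and brings laboratory data into line with vital signs. The same edit can correct Section 9.1.3, which labels the Day +1 samples as baseline tests.

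For any subject already sampled only at Visit 1, report the baseline day and the time since last contrast beside the change results.

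The cost is a small amendment and a change to the laboratory manual. The number of central samples per dosed subject stays the same, and eligibility still rests on the local eGFR. The downside is that subjects with a separate Visit 1 who need a local creatinine then have blood drawn before dosing on two days, and those with a separate Visit 1 have no central result before dosing.
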